4.3 Arm B: Temporising Device Alone - (Control)

Temporising Device Alone

Infants allocated to the temporising device arm (Arm B) will undergo the standard surgical procedure to insert either a VAD or VSGS, at the discretion of the treating surgeon, in line with their standard current practice. Both VAD and VSGS are associated with the same operative and post-operative risk, namely infection, recurring haemorrhage inside the ventricles, new haemorrhage related to ventricular decompression, catheter blockage, failure of absorption of

CSF from the subgaleal pocket of a ventricular-subgaleal shunt, seizures, external leakage of CSF, electrolyte disturbance and a very small risk of stroke. In our experience, all these are rare and occur in less than 5% of cases. The management of these risks will remain at the discretion of the treating neurosurgical team.

4.4 **Concomitant Care**

Premature infants are at risk of multiple medical problems involving many organ systems. Therefore, any concomitant treatments needed by the infant during the study period are permitted. These infants are typically on multiple medications, and data on their administration is beyond the remit of this study. However, details of prescribed prophylactic antibiotics and anti-epileptic medications must be recorded as per section 3.6 (Trial Visits).

4.5 **Unblinding**

Due to the study design, only the primary outcome assessor and individuals making strategic decisions for the trial including the Trial Statistician and the Clinical Project Manager will be blinded to the treatment arm. Therefore, emergency unblinding is not necessary.

Protocol Treatment Discontinuation

In consenting to the trial, parent/legal guardian(s) of participants are consenting to the infant's trial procedure (either Arm A NEL with Temporising Device or Arm B Temporising Device alone), trial follow-up and data collection. However, an individual parent/legal guardian can request to stop trial follow-up and data collection early for any of the following reasons:

- 1. Any change in the participant's condition that in the clinician's opinion justifies the cancellation of planned trial surgery.
- Withdrawal of consent for participation in the trial by the parent/legal guardian(s)
 The participant never underwent standard of care insertion of a temporising device.

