- 4. Any change in the participant's condition that in the clinician's opinion justifies the discontinuation of trial follow-up after the surgery has been completed.

Intra-operative discontinuation of the NEL (due to complications or technical difficulties as listed in the operative CRF) does not mandate removal of the participant from the trial. Any subsequent treatment following intra-operative discontinuation of the NEL will be at the treating clinician's discretion.

As participation in the trial is entirely voluntary, the parent/legal guardian(s) may choose to discontinue participation of their infant for trial follow-up and data collection at any time without penalty or loss of benefits to which they would otherwise be entitled. Although not obliged to give a reason for discontinuing participation, a reasonable effort should be made to establish this reason, whilst remaining fully respectful of their rights.

It should be clear to the parent/legal guardian(s) and recorded in the patient notes what aspect(s) of the trial the participant is discontinuing their participation. These could include:

- Early cessation from sample collections
- Early cessation from questionnaires
- Early cessation from further trial follow-up
- Early cessation electronic health record use.

Patients should remain in the trial for the purpose of follow-up and data analysis (unless the parent/legal guardian(s) withdraws their consent from all stages of the trial). If a patient ceases follow-up early, refer to Section 5.5.

Data on patients who stop follow-up early will be kept and included in analyses where possible. Infants that are withdrawn by their parent/guardian(s) after having had their baseline data collected, but prior to randomisation, will be recorded as withdrawals. As they will not have been randomised, they will not count towards the target sample size though their baseline data will still be summarised at the reporting stage. Infants who are withdrawn after they have

undergone surgery (either Arm A NEL with Temporising Device or Arm B Temporising Device alone), will not be able to withdraw from the surgical part of the trial, only from trial follow-up visits. Participant's parent/guardian(s) will be fully advised of this at the time of consent for the trial and the time of consent for the surgical procedure.

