5.5 Early Stopping of Follow-up

Infant's parent/guardian(s) may withdraw from the trial intervention between time of consent and prior to surgery. After this point, the infant will have received the trial intervention or control (depending on the arm they were randomised to).

If a parent/legal guardian(s) chooses to discontinue their infant's participation in the trial, they should always be followed up they should continue to be followed up as closely as possible to the follow-up schedule defined in the protocol, providing they are willing. They should be encouraged and facilitated not to leave the whole trial. If they do not wish to remain on trial follow-up, however, their decision must be respected, and the participant will be withdrawn from the trial completely. The CCTU should be informed of this in writing using the appropriate documentation. Participants stopping early may have a negative impact on trial data integrity and the ability to reach the stated outcome measures. Every appropriate effort will be made by the investigators to encourage participants to agree to completion of the primary outcome assessment.

Data already collected during the infant's participation in the trial will be kept for analysis. Any optional consent e.g., future use of stored samples already collected can be refused when leaving the trial early (but this should follow a discussion).

Parent/legal guardian(s) may change their minds about stopping their infant's trial follow-up at any time and re-consent to participation in the trial.

Participants who cease post-randomisation trial follow-up early will not be replaced.

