5.6 Loss to Follow-up

If a participant's parent/legal guardian(s) is no longer contactable and has missed at least one follow-up visit within the protocol defined visit window (please refer to Participant Timelines for specific follow-up visit windows), then site staff should attempt to contact the participant's parent/legal guardian(s) at least three times over three months before they are declared as lost to follow-up. Attempts should be made to contact the participant's parent/legal guardian(s) via two different methods of contact (i.e., telephone and letter). Site staff may identify and contact the participant's registered GP to obtain up to date contact information and may also contact their paediatrician at their local hospital and/or neonatal unit. A death form should be submitted if the site becomes aware that the patient has died.

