10.2.2 Ethics Committee Approval

Following main REC approval and Health Research Authority (in England) approvals and before initiation of the trial at each clinical site, the local information pack will be submitted to each Trust's Research and Development (R&D) office by UCL CCTU. The local information pack will contain the protocol, all informed consent forms, and information materials to be given to the prospective participant, the Clinial Trial Site Agreement, the Organisation Information Document (OID), and the validated Schedule of Events Cost Attribution Template (SoECAT). In Wales and Scotland, the R&D office will be asked to give approval. In England, the R&D office will be asked to confirm capacity and capability. Any further substantial amendments will be submitted and approved by the main REC and HRA.

The rights of the participant's parent/legal guardian(s) to refuse to their child to participate in the trial without giving a reason must be respected. After the participant has entered the trial, the clinician must remain free to give alternative treatment to that specified in the protocol, at any stage, if s/he feels it to be in the best interest of the participant. The reasons for doing so, however, must be recorded; the participant will remain within the trial for the purpose of follow-up and data analysis according to the treatment option to which they have been allocated. Similarly, the participant's parent/legal guardian(s) must remain free to change their mind at any time about the protocol treatment and trial follow-up without giving a reason and without prejudicing their further treatment.

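### Section 4.6 mixes reasons for not having the operation with reasons for ending follow-up, and its reason 4 contradicts the protocol's own rule that infants stay in follow-up unless consent is withdrawn

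*Protocol*

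**What the plan says.** Section 4.6 falls between 4.5 (Unblinding) and 4.7 (Compliance and Adherence). Its title concerns discontinuing treatment, but its list is introduced by the statement that "an individual parent/legal guardian can request to stop trial follow-up and data collection early for any of the following reasons". The four reasons are:

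1. "Any change in the participant's condition that in the clinician's opinion justifies the cancellation of planned trial surgery".
2. Withdrawal of consent by the parent or guardian.
3. "The participant never underwent standard of care insertion of a temporising device".
4. A change in condition that the clinician considers "justifies the discontinuation of trial follow-up after the surgery has been completed".

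Other rules bear on the same question:

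- **Later in 4.6:** infants should stay in the trial for follow-up and analysis unless the parent withdraws consent from all stages. An NEL abandoned during surgery does not require removal. Parents may stop at any time without a reason, and may stop samples, questionnaires, follow-up or health-record use separately.
- **5.5:** follow-up continues as close to schedule as possible if the parents are willing. Where they are not, "the participant will be withdrawn from the trial completely".
- **10.2.2:** if the clinician gives a different treatment, "the participant will remain within the trial for the purpose of follow-up and data analysis".
- **8.3.6:** the primary analysis includes only randomised infants with 2-year data.
- **8.2.3:** the treating team is unblinded, and parents learn the arm after the procedure.

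**The concern.** A site with a deteriorating infant can cite 4.6 in either direction. Reason 4 treats the infant's condition as grounds for ending follow-up, while the rule further down says that only full withdrawal of consent does so. Reasons 1 and 3 explain why an operation did not happen. They do not explain why the 2-year assessment should be lost, yet they stand in a list of grounds for stopping data collection.

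The primary outcome is measured once, at 2 years' corrected age, and infants who leave are not replaced (5.5). If exits follow prognosis, and especially if they differ by arm, the infants analysed are no longer comparable as randomised. A missing Bayley assessment cannot be recovered at the analysis stage, whatever method is chosen there.

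Section 5.5 adds a smaller problem. By moving a family that declines follow-up visits straight to complete withdrawal, it bypasses the separate options in 4.6, such as continued health-record use.

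**Working it through.** **Step 1: the rules side by side.**

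| Situation after randomisation | Reasons in 4.6 | Other rules |
|---|---|---|
| Surgery cancelled or no device inserted | Grounds to stop follow-up (1, 3) | Stay in follow-up unless consent is withdrawn from all stages (4.6) |
| Clinician judges that the condition has changed | Grounds to stop follow-up (4) | Same rule in 4.6; continue if parents are willing (5.5); stay in by allocated arm if treatment changes (10.2.2) |
| Parent declines follow-up visits | Partial cessation, item by item | Complete withdrawal (5.5) |

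The two columns cannot both be followed. The conflict is sharpest inside 4.6 itself.

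**Step 2: the plan's own figure (8.1).** Inputs: control CQ = 100 × Beta(1,1); NEL CQ = 100 × Beta(10, 4.25); 45 infants per arm; two-sided Wilcoxon test at 5%; 10% loss. Simulated power is 91.0% (normal approximation, 10,000 replicates) and 91.2% (exact, 3,000 replicates), against 90% stated. The model medians are 50 and 71.1. Recruitment: 90 / (1 − 0.10) = 100. The plan's figure reproduces, and it leaves room for 100 − 90 = 10 losses.

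**Step 3: random loss.** With no true difference (both arms uniform on 0 to 100, 50 per arm), losing 10 infants at random gives a type I error of 5.1% to 5.2%, whether they are split 5 and 5 or all come from one arm. Under the planned effect, random loss of 5 per arm leaves power at 91.0%. The 10% allowance works if loss is unrelated to outcome.

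**Step 4: worst-case selective loss, no true difference.** Remove the k lowest scorers from one arm only. In a uniform sample of 50, the expected value of the j-th smallest score is 100 × j / 51. The full arm's median is then 100 × 25.5 / 51 = 50. After removal it is 100 × (25.5 + k/2) / 51. The false median difference is therefore 100 × (k/2) / 51, or about 0.98k points. For k = 5 this is 250 / 51 = 4.9.

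| k lost, one arm | False median difference (simulated) | Type I error |
|---|---|---|
| 0 | 0.0 | 4.9% |
| 2 | 2.1 | 7.2% |
| 3 | 2.9 | 8.5% |
| 5 | 4.9 | 14% |
| 10 | 9.9 | 37% |

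Losing the 5 lowest in each arm gives about 8% and no average median difference.

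**Step 5: the same loss under the planned effect.** With 50 per arm and no loss, power is about 94%. Losing the 10 lowest in control only cuts it to about 55% and the mean median difference to about 11. Losing the 10 lowest in the NEL arm only raises them to about 98% and 24. The bias can run either way.

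**The case against.** The strongest reply is that the list gives the team no power at all. Its lead-in makes the stop a parental request, and parents may already leave at any time without a reason. Deleting reasons 1, 3 and 4 would close no exit. A reader might infer that unblinded clinicians may themselves end an infant's follow-up; the text does not say so, and the point is not put that strongly here. What stands is that reason 4 presents a clinician's judgement of the infant's condition as accepted grounds for stopping follow-up, against the rule lower in the same section.

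Four other stronger readings also fail:

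- **Reasons 1 and 3 as a large source of loss.** Randomisation takes place after the infant has reached theatre (4.1), so most cancellations would precede it, and parents do not yet know the arm. Reason 4 is the main exposure.
- **A breach of the intention-to-treat rule.** The sentence in 8.3.6 applies to other analyses where possible, and the same section makes the primary analysis complete-case. The conflict is with the follow-up rules.
- **Section 5.5 as a plain exit.** It first asks that families be encouraged to stay and to complete the primary assessment, and it allows re-consent at any time. Complete withdrawal comes last. The mismatch with the partial options in 4.6 remains.
- **Section 5.6 as declaring families lost after one missed visit.** It also requires that the parents can no longer be contacted, and that sites try "at least three times over three months before they are declared as lost to follow-up", by two methods. It does not forbid a new approach at 2 years. A further attempt is a retention preference, not the correction of an error.

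**Conclusion.** The contradiction is real. Section 4.6 gives incompatible instructions about infants whose condition changes or whose operation does not take place, and 5.5 does not match its partial-cessation options. Following reason 4 as written would permit loss related to prognosis in a complete-case analysis of a single measurement.

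The size is unknown. The protocol gives no rate or direction for such exits. The figure of about 14% type I error and 5 false points (a quarter of the 20-point target) assumes no true effect, uniform scores in both arms, and that exactly the 5 lowest scorers leave one arm and none leave the other. That is the extreme, and less selective or balanced loss gives less. A reader might take 14% as the expected consequence of this list. It is not: it illustrates informative loss in general and does not isolate what the list adds to the exit parents already have.

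**What to change.** - **4.6, reasons 1 and 3:** state that they are reasons for not receiving the trial operation, and that infants already randomised stay in follow-up to the 2-year Bayley assessment. The decision whether to operate is untouched.
- **4.6, reason 4:** delete it, so that parental withdrawal of consent is the only route out of follow-up. Parents keep their right to stop at any time without a reason.
- **5.5:** replace complete withdrawal with the stepwise options of 4.6, and add a specific request for the 2-year assessment.
- **5.6 (optional):** require one further contact attempt before the 2-year window for families earlier declared lost.

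The cost is a wording amendment and a few more contacts by site staff, with no new visits. The downside is that some families will be contacted again at about 2 years.

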4.7 Compliance and Adherence

The PI at the participating site is responsible for compliance and adherence to the trial protocol.

4.7.1 Trial Intervention (NEL with Temporising Device)

The ENLIVEN-UK trial surgical intervention is performed once by a suitably qualified paediatric neurosurgeon who is a member of the site team. All paediatric neurosurgeons delegated to perform the surgical intervention in ENLIVEN-UK must be experienced in infant neuroendoscopy and NEL and must attend a dedicated trial training session on the NEL procedure arranged by the Sponsor. Therefore, non-compliance with the intervention is not anticipated but trial data will be reviewed on a monthly basis and post-operative ultrasound scans, will be reviewed at least quarterly by the TMG to evaluate any variability in the surgical procedures. Where necessary, feedback will be given to the PI at the participating site regarding their operative technique and radiographic outcome. Any relevant issues will be discussed with the participating unit.

4.7.2 Telephone Interviews for Adapted Client Service Receipt Inventory (CSRI children version)

A telephone interview with the infant's parent/guardian(s) should be conducted by a member of the research team at site to complete the Adapted Client Service Receipt Inventory (CSRI children version) at 3-6-,12-, 18-months' and 2 years' corrected age listed in Table 3. These telephone interviews will be performed every 6 months. At each visit timepoint, at least four attempts to contact the infant's parent/guardian(s) should be made over the course of 48 hours, twice a day. On failure to obtain a response by telephone, the CSRI questionnaire will be sent out to the participants by post.

4.7.3 Questionnaire Completion by infant's parent/guardian(s)

The infant's parent/guardian(s) should complete the EuroQoL EQ-5D-5L, TNO-AZL TAPQOL, Q-CHAT, BITSEA questionnaires at the timepoints listed in Table 3. These should be completed and returned to a member of the research team during attendance at the relevant follow-up visits. In cases where it is not possible to complete the questionnaires during the follow-up visit, they can be returned to the research team by post using a self-addressed envelope.

Questionnaires should be completed at the start of the visit before any other procedures are performed. The completed questionnaire responses to the EQ-5D-5L must be reviewed during the visit to check for self-reported 'severe' or 'extreme' anxiety and depression. Parents/guardians reporting these symptoms should be signposted to access support from their healthcare provider e.g., their GP.

In cases where the questionnaires have been returned to the research team by post, the EQ-5D-5L responses must be assessed by a member of the research team as soon as they are received to check for self-reported 'severe' or 'extreme' anxiety and depression. Parents/guardians reporting these symptoms should be contacted and signposted to access support from their healthcare provider e.g., their GP.

4.8 Eligibility Criteria for Individuals Performing the Interventions

NEL for this indication has undergone an evolution from its initial descriptions. All participating surgeons have been involved in a consensus meeting where the steps of the procedure, permitted variations and endpoints were agreed upon to ensure internal consistency (28) Participating surgeons are experienced neurosurgeons and endoscopists who routinely use endoscopic techniques in their clinical practice.

Paediatric neurosurgeons performing the surgical interventions for ENLIVEN-UK must be experienced in infant neuro-endoscopy and NEL and must attend a dedicated trial training session on the NEL procedure arranged by the sponsor. UCL CCTU will maintain a central training log for all investigators delegated to perform surgical procedures in the trial.

Nursing staff, medical staff, and any other delegated members of the clinical trial team at participating sites should have the appropriate qualifications to manage patients with IVH and PHVD. Protocol-specific training will be provided to participating sites by the ENLIVEN-UK Trial Manager or delegate at UCL CCTU prior to site activation, or during a Site Initiation Visit (SIV). New site staff who start work on the trial after site activation occurs will be provided with protocol specific training prior to performing trial related procedures.

Each member of the trial team at each participating site will have roles delegated by the PI and documented on the ENLIVEN-UK site delegation log. Current CVs and GCP certificates of all individuals working on the trial will be collected by the ENLIVEN-UK trial team at UCL CCTU to document their qualifications and relevant experience.

5 Assessments & Follow-Up

5.1 Outcomes

5.1.1 Primary Outcome(s)

The primary outcome measure is the CQ measured at 2 years' corrected age following addition of NEL to the standard of care. We aim to detect a 20-point (clinically significant) difference in CQ at this timepoint. The CQ is measured by dividing the age equivalent cognitive score on the Bayley Scales of Infant and Toddler Development (4th edition) (Bayley IV) by the corrected age at assessment (both in months) multiplied by 100. A 20-point difference is the equivalent of 4.8 months' advantage at 2 years of age (and two years' difference at 10 years of age).

The Bayley Scale will be administered by a qualified and validated independent clinical development specialist blinded to the treatment arm and performed at its own separate visit.

5.1.2 Secondary Outcomes

The secondary outcome measures are:

- 1. Developmental Measures:
 - a. Motor quotient (MQ): Age equivalent motor score of the Bayley IV divided by corrected age at assessment, measured at 2 years' corrected age
 - b. Language quotient (LQ): Age equivalent language score of the Bayley IV divided by corrected age at assessment, measured at 2 years' corrected age
- 2. Other neurological and functional assessments conducted during the 2-year follow-up visit:
 - a. Presence of seizures during the first 2 years and use of anticonvulsant medication at 2 years.
 - Presence of cerebral palsy (+ accompanying Gross Motor Function Classification System (GMFCS) grade and deficit distribution map using the Classification of SCPE
 - c. Assessment of hearing and vision (British Association of Perinatal Medicine classification)
 - d. Parent report:
 - i. Brief Infant Toddler Social Emotional Assessment (BITSEA)
 - ii. Quantitative Checklist for Autism in Toddlers (Q-CHAT)
- 3. Mortality up to 2 years corrected age.
- 4. NEL & VP shunt related outcomes:

- a. Safety of NEL: Number of Adverse Events, where Adverse Events would include (and not limited to) secondary bleeding in the brain, post-operative infections, temporising device survival, mortality, stroke, seizures, electrolyte disturbances, CSF leak, unexpected readmissions or return to theatre.
- b. Number and type of further surgical procedures, including revision of the temporising drainage device (VAD or VSG), addition of a second temporising device, surgery for loculated or isolated ventricles, and revisions of the VP shunt, if implanted, until two years' corrected age. These infants often need multiple shunt revisions during their first two years of life. We will have a separate CRF to record data related to these unexpected presentations and procedures.
- c. Requirement for permanent VP shunt insertion at 6 months' corrected age. (This is at the discretion of the treating team in the participating centre, according to routine clinical care).
- 5. Quality of life and health economic assessments:
 - a. Health-Related Quality of Life (HRQoL) in children: TNO-AZL Preschool Children's Quality of Life (TAPQOL) to be assessed at 12-months and 2 years' corrected age
 - b. HRQoL in primary caregiver: EuroQoL EQ-5D-5L to be assessed at baseline, 6 months, 12 months- and 2 years' corrected age
 - c. Healthcare resource use costs (CSRI (adapted) children version)⁴⁵ (via telephone assessment) at 3-6-,12-, 18- months and 2 years' corrected age.
 - d. Subsequent cost-effectiveness analysis & cost-benefit analysis of impact on carers based on responses to the EQ-5D-5L

35

